6.2 STUDY MONITORING

Since there is no data to be reviewed regularly in this behavioral trial and no stop-rule, as the main concern being loss of confidentiality, the PI will have access to an existing URBAN ARCH Data Safety Monitoring Board (DSMB) if issues arise as needed for the R00 SCRIPT pilot behavioral intervention trial. If there are no issues, the DSMB will not review.

General description of URBAN ARCH DSMB

To ensure the safety of the participants and the validity and integrity of the data, the URBAN ARCH consortium established an external DSMB to assume oversight of the entire URBAN ARCH Consortium and any studies originating from the URBAN ARCH Cohorts, in accordance with NIH guidelines. The K99 used URBAN ARCH data for its quantitative analysis, and the R00 study originated from this work. Although risks with the R00 SCRIPT pilot behavioral intervention trial are essentially limited to loss of confidentiality, due to the vulnerable population of HIV-positive and substance using individuals, the URBAN ARCH DSMB can advise on special precautions to ensure the safety of all R00 study participants. Should any issues be raised by either the PI, any co-investigator or any key study personnel in the R00 SCRIPT behavioral intervention trial, the PI will consult with the URBAN ARCH DSMB. The URBAN ARCH DSMB is responsible for ensuring participant safety (by reviewing blinded and unblinded safety data on a regular basis and assessing the safety of study procedures) and for monitoring the overall conduct of the URBAN ARCH studies.

The DSMB is an independent group advisory to the URBAN ARCH PIs and the NIAAA, and is required to provide recommendations about starting, continuing, temporarily suspending the trial until certain conditions are met, and stopping the studies. Most importantly for the SCRIPT interventional behavioral trial, the DSMB can be asked to make recommendations, as appropriate, about:

- Benefit/risk ratio of procedures and participant burden
- Selection, recruitment, and retention of participants
- Protocol violations and adherence to protocol requirements
- Completeness, quality, and analysis of measurements
- Amendments to the study protocol and consent forms
- Participant safety
- Notification of and referral for abnormal findings

The DSMB meets by conference call at a minimum of every 6 months. The Board is charged with evaluating the quality of trial administration, monitoring safety issues, and providing guidance on scientific, methodological and ethical issues. Specifically, the Board reviews investigators' plans and processes for

identifying individual or patterns of adverse events and review accumulating safety data. Following each meeting, the DSMB will make recommendations on modification, or termination of the study.

The Board will be composed of three full members (inclusive of the DSMB Chair) and 1 adjunct member.

Full Members of the DSMB are:

1. [name] (Professor of Epidemiology and Biostatistics, BUSPH), Chair of DSMB
2. [name] (Professor of Medicine, Brown Medical School)
3. [name] (Associate Professor of Psychology, Indiana University-Purdue University Indianapolis)

Consulting with the DSMB as needed for this trial will be valuable for further ensuring the quality and scientific validity of the study. An agenda will be provided detailing the studies to be discussed. If any issues arise with the R00 SCRIPT study, it will be added to the agenda. It is estimated that the meeting will be scheduled for 1.5 hours. Communication in the interim will be as needed. Unscheduled meetings can be requested by any party with the responsibility of overseeing the study. Requests can be made to the DSMB Chair, PIs, or NIAAA officials. The Chair, in collaboration with the URBAN ARCH Administrative Coordinating Core or NIAAA, will schedule any unplanned meetings.

The Methods and Time for Assessing, Recording, and Analyzing Safety Parameters

All AEs will be assessed to determine if they meet criteria for a Serious Adverse Event (SAE). All AEs will be reported to [name] at weekly phone meetings. [name] will be designated to distinguish a serious adverse event (SAE) from a non-serious adverse event. The site PI and project manager (both MDs) will monitor SAE and AE on site. If the AE is serious, then the SAE form must be completed and appropriate reporting measures followed. Investigators are encouraged to consult with the PI, if they are uncertain how to classify an event.

Suicide Safety Protocol: Any participant who voices current suicidality or is experiencing a psychiatric emergency during the interview or group session in the presence of a Research Assessor or Interventionist, will be reported to the site PI or his designee immediately. The site PI or the assessor (Research Assessor or Interventionist) will determine the appropriate course of action, which will depend on location of the event and the clinical situation. If clinically indicated, the participant will be referred to acute suicide intervention services.

- Information of risk for suicide may be obtained by either impromptu information, from question 9 of the Mental Health Survey: PHQ-9 in the study assessment, or question 1f in Section B of the screener.
- If the participant answers any option that is not “Not at all” for question 9, a suicide safety question will autopopulate, assessing suicidal plans. If the participant answers “Yes” or “Refused” for the suicide safety question, the Research Assessor will move forward with the above suicide safety protocol.
 - If the participant answers “Yes” or “Refused” for the suicide safety question (post question 9 of the PHQ-9) during the baseline assessment, the participant will be disenrolled from the study. They will not be disenrolled during the 1-month or 6-month assessment, as they will no longer be receiving the intervention, however they will still be clinically assessed.
- If a potential participant answers “Yes” or “Refused” for question 1f of section B of the screener, the Research Assessor will move forward with the above suicide safety protocol.

The study will take place in a setting where standard procedures are in place to assist patients who experience acute events. The research assessors and interventionists are trained clinical psychologists, specialists in social work, and addiction psychiatrists. If consequences arise due to research procedures (e.g., distress, anxiety, suicidal ideation), the physician investigators will be available to assess participants and make appropriate interventions or referrals based on the clinical circumstances. Any participant who voices current suicidality or is experiencing a psychiatric emergency during the assessments will be evaluated by that physician investigator, who will determine the appropriate course of action, which will depend on location of the event and the clinical situation. Patients will be escorted to receive care by appropriate staff if deemed necessary.

- If an event is discovered outside of the scheduled study visits, it must still be recorded accordingly.
- Action to be taken will be determined by the RAs for all AEs that are mild and moderate (unless specified below) and by the site PI or project manager for SAEs and AEs that are severe, life-threatening or fatal.

SAE Reporting

If the SAE is not resolved or stabilized at this time or new information becomes available after the SAE form is completed, the SAE form should be updated as soon as possible. Any changes or updates to the SAE form will need to be re-reviewed and re-authorized by the study clinician.

In some cases, the study clinician may be unsure upon first learning of an SAE whether it is study related and/or expected, because study staff are awaiting more complete medical records. In such cases, the study clinician should make his/her best estimate of relatedness and expectedness, understanding that these determinations can be updated later. When updating determinations at a later date, the rationale for the change should be included in the SAE narrative.

SAEs and unanticipated events which are considered “at least possibly related” during the treatment and follow-up phases will be reported to the local IRB and to NIDA within 48 hours of knowledge of the SAE and all other SAEs and unanticipated events will be reported within the time period mandated by the local IRB as indicated below.

The site must actively seek information about the SAE until the SAE is resolved, stabilized or until the participant is lost to follow-up and terminated from the study.

To summarize: upon determining an Adverse Event is Serious, the following procedures should be followed:

- The study staff, while meeting/talking with the participant or person providing details on the event, will gather as much information about the event from the participant as possible and complete the appropriate forms.
- The completed AE and SAE forms will be reviewed by key personnel on the Pavlov team. Any relevant clinical documents (labs, physician notes) available at that time will be provided to key personnel on the Pavlov team within 24 hours of finding out about the event.
- After initial notification, the SAE must be updated with any additional information.

All unanticipated problems must be reported to the US team immediately.

Reporting Procedures to the IRB and NIDA

Each site will follow reporting guidelines set forth by their Institutional Review Boards regarding unanticipated problems, adverse events, and serious adverse events. Deaths and serious breaches of confidentiality reported to research staff will be reviewed by the site PI and reported to the PI the same day, who will then report to the IRB. The co-investigators and PI will review aggregate data every 6 months. Should any irregularities arise, the PI will consult with the DSMB, as described above. According to the minimum standards for AE and SAE reporting to NIDA, we will report AEs and SAEs once per year through the annual progress report.

Reporting mechanisms of IRB actions to NIDA: The PI will provide a summary of safety-relevant events to NIDA on an annual basis as part of the progress report.

Report of changes or amendments to the protocol. All changes or amendments to the protocol will be submitted to both IRBs prior to changing study procedures.

BUMC Reporting Guidelines:

The Principal Investigator at BMC/BU Medical Campus will report Unanticipated Problems and Adverse Events to the BMC/BU Medical Center IRB in accordance with IRB policies:

- Unanticipated Problems involving a fatal or life-threatening event will be reported to the IRB within 2 days of the investigator learning of the event.
- Unanticipated Problems not involving a fatal or life-threatening event will be reported to the IRB within 7 days of the investigator learning of the event.
- Adverse Events (including Serious Adverse Events) will be reported in summary at the time of continuing review, along with a statement that the pattern of adverse events, in total, does not suggest that the research places subjects or others at a greater risk of harm than was previously known.

Pavlov Reporting Guidelines:

What Event is Reported	When is Event Reported
Fatal or life-threatening unexpected, suspected serious adverse reactions	Within 7 calendar days of initial receipt of information
Non-fatal, non-life-threatening unexpected, suspected serious adverse reactions	Within 15 calendar days of initial receipt of information
AEs and UPs	On a quarterly basis

7. DATA MANAGEMENT

7.1 DATA COLLECTION

All study data will be captured electronically on computers via a secure, web-based data capture system. All computers for data collection and analysis will have encryption. Audiorecordings to code adherence to the study protocol and the study manual will be made with a dedicated, portable audiorecorder. Recordings will be transferred to a secure server immediately following the session and deleted from the portable device. Coding will be directly from audiorecordings by a Russian-speaking, certified ACT trainer. All audiorecordings

will be kept on the secure server until seven years after completion of study analyses and publication of study manuscripts and then deleted.

7.2 QUALITY CONTROL PROCESS

Quality control measures will include: detailed and unambiguous specifications for completion of data forms, including rules for coding skipped questions and missing data, training of study staff responsible for data collection and built-in validation rules, error checks, question skips for electronic data capture, and computer algorithms to check for out-of-range codes and internal inconsistencies. All data, regardless of capture method, will be converted to SAS datasets and reviewed for logic, skip patterns, response ranges, out-of-range codes, and internal inconsistencies. The RAs will be queried regarding any noted inconsistencies.

7.3 DATA SECURITY, WEB SYSTEMS, AND CONFIDENTIALITY

Screening forms and most other research paperwork will not include the participant's name; instead, a unique ID will be assigned to each person screened, and another number assigned to those who enrolled. Any documents with identifiable participant data will only be accessible to the Russian Co-Investigators, the project management staff, and the RAs who recruit and follow participants.

Tracking information will be kept similarly. Computer data will be password protected, and accessible only to research associates needing the information for follow-up purposes.

The Ukrainian Institute on Public Health Policy (UIPHP) will design, develop and maintain the electronic data collection forms, participant and data tracking, and underlying database systems, and implement procedures for data quality control, including multiple checks for entered data. Electronic data collection forms will be designed to read easily, have clear instructions, preprogrammed skip patterns, real-time range checks and internal logic to minimize missing data and result in "cleaner" data at capture. Electronic data collection forms, including randomization module, participant and data tracking, will be developed in REDCap (Research Electronic Data Capture), a web application located at UIPHP server. The REDCap platform has no hard requirements with regard to server processing power, memory or hard drive space since it is not resource-intensive and requires very little initial drive space by either the web server or database server. The application employs various methods to protect against malicious users who may attempt to identify and exploit any security vulnerabilities in the system. The REDCap users have access only to data and information that they are supposed to have within the application by identifying user privileges. Each user has their own account, and their user account will only have access to REDCap projects that they have created themselves or to projects which other users have granted them access. REDCap contains an auto-logout setting, which is customizable (default auto-logout time is 30 minutes), and will automatically log a user out of the system if they have not had any activity (e.g. typing, moving the mouse) on their current web page for the set amount of time. This prevents someone else from accessing their account and their project data if they leave a workstation without properly logging out or closing their browser window. REDCap maintains a built-in audit trail that logs all user activity and all pages viewed by every user, including contextual information (e.g. the project or record being accessed). Therefore, a REDCap project administrator will be able to monitor any activity in the project, e.g. entering data, exporting data, modifying a field, running a report, or add/modifying a user. Study forms will be completed according to the schedule below.

After completion of data collection in REDCap, all data that we collect from participants will be de-identified and transferred to the URBAN ARCH repository for future research. When investigators want to perform a study on repository data they will submit a study plan for review and approval and will need to obtain any necessary approvals, such as approval from their IRB, to carry out the work with repository data. Prior to receiving the data, the researchers will agree not to share the data and not to attempt to identify any individual participants. In all cases, the data will be released from the repository in coded form (i.e., names and contact details will not be included and data/samples will be identified by a subject ID number).

FORM	Phone Screen	Screen & Baseline Visit		ACT Sessions 1-3	1-month visit (4 weeks)	6-month visit (24 weeks)	As Needed
	Screen	Screen	Baseline				
	X	X					
Screener	X	X					
Consent and enrollment form		X					
Contact info			X	X	X	X	X
Baseline assessment			X		X	X	
1-month assessment					X		
6-month assessment						X	
Contact log							X
Baseline tracking form			X				
Follow-up tracking form			X	X	X	X	
Participant tracking overview							X
SAE form (Web)							X
Incarceration Form							X
Study conclusion form							X
ACT interventionist fidelity checklist				X			X
All forms are electronic, unless indicated otherwise							

8. STATISTICAL ANALYSIS

This study will use an intent-to-treat analysis that includes all participants according to their randomized assignment. Descriptive statistics will be calculated for variables at baseline and each follow-up time to assess whether there appear to be any differences across treatment arms.

Our Specific Aims are to compare the effects of SCRIPT and standard of care on following outcomes:

Aim 1: Evaluate the feasibility of an ACT stigma intervention compared to standard of care via a 2-armed RCT of 100 HIV-positive Russian PWID on the following outcomes:

- Primary: Satisfaction with the intervention at 1 month
- Secondary:
 - Participation in three intervention sessions;
 - Fidelity to the intervention, using the Adherence Raters' Manual for Stigma Treatment Study (Kohlenberg et al, 2004) and an intervention adherence score

Aim 2: Measure changes in internalized stigma

Primary:

- a. HIV Stigma via the Simbayi HIV internalized shame scale at 1 month;
- b. Substance Use Stigma via Modified Substance Abuse Self-Stigma Scale at 1 month

Secondary:

- a. Any initiation of HIV care (ART) at 6 months
- b. Engagement in substance use care at 6 months
- c. Change in last 30 days injection drug use at 6 months

Exploratory:

- a. Depression as measured by the PHQ-9 at 6 months
- b. Anxiety as measured by the GAD-7 at 6 months
- c. Intersectional stigma as measured by both substance use stigma and HIV stigma scales at 6 months
- d. Psychological flexibility measured via the Acceptance and Action Questionnaire at 6 months

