2.3 STUDY OUTCOMES

Aim 1. The primary outcome for aim 1 is satisfaction with the intervention at month 1, assessed by a satisfaction scale. Secondary outcomes are participation in intervention sessions and fidelity to the intervention, assessed via audio-recording. This will be scored with an ACT Adherence Checklist and the Adherence Raters' Manual for Stigma Treatment Study (Kohlenberg et al, 2004) to rate the recorded intervention audio recordings.

[figure not shown]
Aim 2. The primary outcome for aim 2 is measured change in internalized HIV stigma and substance use stigma at 1 and 6 months assessed by the Berger HIV Stigma Scale, the Leickness HIV internalized shame scale, the modified Substance Abuse Self-Stigma Scale, and the Acceptance and Action Questionnaire – Substance Abuse. Secondary outcomes are initiation of ART, recent (last 30 days) injection drug use frequency at 1 and 6 months, and mental health as measured by the PHQ-9 and GAD-7.

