2.4 STUDY DESIGN

SCRIPT is a Randomized Controlled Trial (RCT) among 100 HIV+ PWID, which aims to test the feasibility of the SCRIPT intervention and evaluate its effectiveness on the reduction of internalized stigma as well as self-reported entry into substance abuse treatment or initiation of ART. Eligible participants will be randomly assigned into one of two groups: 1) Control group receiving CSO site standard of care or; 2) ACT intervention. Both the intervention group and the control group will receive standard of care counseling and referral to addiction treatment and HIV treatment at the CSO sites. Following their baseline assessment, participants assigned to the intervention group will meet with the interventionist three times over one month in approximately 13 groups of 5 people each. All three sessions will be in groups, except for the occasional individual make-up 2nd session (more details in section 3.6B). Study outcomes will be assessed at 1 and 6 months (Figure 1).

Figure 1 illustrates the design of this 2-arm RCT with 65 participants in the SCRIPT intervention arm and 35 participants in the standard of care arm.

Figure: SCRIPT Study Design

Throughout the course of the study, participants in both groups will be expected to participate in three in-person assessments (baseline, 1 month and 6 months).

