2.7 INCLUSION CRITERIA

To be eligible to participate in the trial, participants will need to meet the following inclusion criteria:

1. 18 years old or older
2. HIV-positive
3. Current injection drug use (past 30 days)
4. Not currently on ART
5. Provision of contact information for two contacts to assist with follow-up
6. Address within 100 kilometers of St. Petersburg
7. Not enrolled in any other research studies
8. Possession of a telephone (home or cell)
9. Able and willing to comply with all study protocols and procedures over 6 months
10. Available at the specific days of the week and times that the group sessions will be occurring for the subsequent 3-4 weeks (to ensure that participants randomized into the intervention arm will be able to receive the intervention)

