3.2 RANDOMIZATION

Randomization is not stratified by any factor. Blocked randomization with randomly selected block sizes was used to reduce selection bias and make the sequence less predictable. We generated a random sequence of 34 blocks, sizes 3 and 6. Then, we randomized assignments within each block with an allocation ratio of 2:1. A greater number of blocks was created than is necessary in the event that the investigator continues enrollment beyond the initially planned sample size. Randomization sequence was created in R, version 3.5.2 (Copyright (C) 2018 The R Foundation for Statistical Computing) and uploaded to REDCap platform, electronic data collection tool.

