5. ASSESSMENTS

5.1 BASELINE ASSESSMENT

The baseline assessment will be conducted immediately following the screening and informed consent. The assessment will be interviewer-administered.

Participants will be assessed as part of this study using validated interview instruments covering the following topics, which will take approximately 60 min:

- Demographics, modified from the ASI Lite-CF Clinical/Training Version and Addiction Severity Index⁷
- ART Medication Use and Adherence
- HIV Sex Risk Behaviors, questions are adapted from the Women's Health Coop Baseline Questionnaire
- HIV Risk Categories, using questions adapted from the American Red Cross and Navaline et al.¹⁷
- HIV Disclosure, using questions from Stein et al. (1998)¹⁸ and Raj et al. (2006)¹⁹
- HIV Stigma, using the Berger et al. HIV stigma scale²⁰ and Leickness et al.
- Substance Use Stigma^{21, 22}, via a modified Substance Abuse Self-Stigma Scale
- Substance Use enacted interpersonal stigma, through the Stigma-Related Rejection Scale (SRS)
- Psychological flexibility, by the Acceptance and Action Questionnaire – Substance Abuse (AAQ-SA)
- Mental health through the Patient Health Questionnaire (PHQ-9)
- Anxiety by the GAD-7
- Partner Violence and Sexual Assault, adapted from the TAJ assessment
- Alcohol Use, via the AUDIT-C²⁸
- Perceived alcohol stigma, using questions from Luoma et al. (2010)
- Drug use by an adapted version of the Risk Behavior Survey^{30, 31}
- Overdose and Suicide, using adapted questions from Britton et al. (2012)³⁴
- Social Support, using the harmonized STTR document^{35, 36}
- VR-12 Health Survey & MOS-HIV^{37, 38}
- Care utilization
- Post-Traumatic Stress Disorder via the Abbreviated PTSD Checklist
- Police involvement
- HIV Testing History

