8.1 PRIMARY ANALYSES

The primary outcome for this aim is satisfaction with the intervention. We will calculate descriptive statistics for all variables at baseline and follow-up. Initial analyses will compare binary outcomes between groups using a chi-square test and comparing continuous outcomes (i.e. satisfaction scores) using two sample t-tests. Because ACT intervention is delivered in the form of group sessions, individuals within the same groups will be correlated. All analyses will use the intention-to-treat approach and analyze participants according to randomized group, accounting for intra-group correlation.

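### Injection use at 6 months has no assigned analysis; if the plan's only continuous-outcome test is run on the change score, it is valid but gives up power against baseline adjustment

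*Combined protocol and SAP*

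**What the plan says.** Sections 2.1 and 8 list, as Aim 2 secondary outcome c, "Change in last 30 days injection drug use at 6 months". Section 2.3 describes the same construct as a level at two visits: "recent (last 30 days) injection drug use frequency at 1 and 6 months". These differ on level versus change and on whether month 1 counts.

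Section 8 says the arms are to be compared on the listed outcomes, so a between-arm estimate is intended. The only methods are in section 8.1, which opens with satisfaction. It describes initial analyses by chi-square test for binary outcomes and, for the rest, "comparing continuous outcomes (i.e. satisfaction scores) using two sample t-tests". It then promises to "analyze participants according to randomized group, accounting for intra-group correlation" but names no model. The plan mentions no baseline adjustment, transformation, count model or rank method.

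The instrument is given in section 5.1 as "Drug use by an adapted version of the Risk Behavior Survey", without its response scale. Section 5.2 schedules drug use at baseline, 1 and 6 months. Section 2.7 requires "Current injection drug use (past 30 days)", so every participant should report some injecting at entry. Section 2.4 plans "65 participants in the SCRIPT intervention arm and 35 participants in the standard of care arm".

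**The concern.** A statistician following section 8.1 literally would take each participant's 6-month value minus the baseline value and compare the arms by t-test. Subtracting the baseline assumes that the 6-month value moves one for one with it. When the correlation between visits is modest, the subtraction adds noise, and the change can vary more than the 6-month value alone. Regression on the baseline estimates that slope instead of fixing it at 1. Under randomisation both approaches estimate the same mean difference between arms, so the loss of precision buys nothing.

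At stake is the width of the interval for one behavioural secondary outcome, with only about 35 controls. Separately, two definitions and no assigned analysis leave the choice of outcome and method open until the data are seen.

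**Working it through.** The documents state no power, alpha, SD, correlation or dropout for this outcome, so there is no figure to reproduce.

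**Inputs.** From section 2.4: 65 v 35. Assumed: two-sided alpha 0.05; true difference 0.4 to 0.6 SD of the 6-month value; baseline to 6-month correlation rho 0.2 to 0.8; equal SDs at both visits, scaled to 1. Session-group correlation was not modelled.

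**Variances.**
- 6-month value: 1
- Change: 2(1 − rho)
- Baseline-adjusted (ANCOVA): 1 − rho²
- Sample-size ratio, change to ANCOVA: 2(1 − rho)/(1 − rho²) = 2/(1 + rho)

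So the change is noisier than the 6-month value only when rho is below 0.5. With unequal SDs, the change variance exceeds the ANCOVA residual variance by (SD_baseline − rho × SD_6-month)², which is never negative.

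**Power.** Power = Φ(d/(s × √(1/65 + 1/35)) − 1.96), where √(1/65 + 1/35) = 0.2097 and s is the square root of the variance above. For d = 0.5 and rho = 0.2:
- Change: s = √1.6 = 1.265; 0.5/(1.265 × 0.2097) − 1.96 = −0.075; power 47%.
- ANCOVA: s = √0.96 = 0.980; 0.5/(0.980 × 0.2097) − 1.96 = 0.47; power 68%.

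| rho | t-test on change | t-test on 6-month value | ANCOVA | sample ratio, change/ANCOVA |
|---|---|---|---|---|
| 0.2 | 47% | 67% | 68% | 1.67 |
| 0.3 | 52% | 67% | 71% | 1.54 |
| 0.5 | 67% | 67% | 79% | 1.33 |
| 0.7 | 87% | 67% | 92% | 1.18 |
| 0.8 | 97% | 67% | 98% | 1.11 |

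Change v ANCOVA at rho 0.2, 0.5 and 0.8 is 33 v 50%, 48 v 60% and 86 v 89% for d = 0.4, and 62 v 83%, 82 v 91% and 99.5 v 99.8% for d = 0.6. With about 15% loss (55 v 30) and d = 0.5, it is 41 v 61%, 60 v 72% and 94 v 96%.

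**Skewed counts, first simulation.** Assumed: negative binomial, mean 25, dispersion 1, baseline at least 1, rate ratio 0.6, 65 v 35, 1,500 runs per cell.

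| observed rho | t-test on change | linear ANCOVA | log(1+count) ANCOVA |
|---|---|---|---|
| 0.17 | 37% | 68% | 52% |
| 0.36 | 46% | 72% | 58% |
| 0.55 | 58% | 82% | 68% |
| 0.77 | 81% | 95% | 90% |

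The loss from using the change score instead of linear ANCOVA is 14 to 31 points. With no true effect, the change t-test rejected in 4.2 to 4.8% of runs, linear ANCOVA in 4.3 to 5.5%, and a robust Poisson model with log baseline in 6.1 to 7.3%.

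**Skewed counts, second simulation.** Assumed: 80% retention (0.8 × 65 = 52, 0.8 × 35 = 28), rate ratio 0.6, latent correlation 0.3 to 0.8, 0 to 20% excess zeros at 6 months. Baseline adjustment beat the change t-test in all 36 scenarios with a true effect, by about 7 to 42 points. Without excess zeros, power of the change t-test ranged from 24 to 88%. In this simulation log(1+count) gained power when there were no excess zeros. With 20% excess zeros it fell to 22–32%, against 30–63% for linear adjustment, and was sometimes below the change t-test.

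**The case against.** The strongest reply is that the plan never says this outcome will be tested by a t-test. Section 8.1 concerns primary analyses, calls the tests initial, cites satisfaction scores, and promises an allowance for correlation that a plain t-test cannot provide. That is correct, so the efficiency loss is conditional. But the alternative reading is that the outcome has no specified analysis, which needs the same repair.

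Second, nothing in the documents says the variable is a skewed count. It could be injections, days, categories or yes/no. If it were yes/no, the entry criterion would make every baseline value a yes; there would be nothing to adjust for, and the chi-square test would apply. The word frequency in section 2.3 points away from that but does not settle it.

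Third, the size of the loss is driven by assumptions. At rho 0.7 to 0.8 the normal-theory loss at 0.5 SD is only 1 to 5 points, and the change score then beats the unadjusted 6-month value. This stands against any single headline figure. It does not reverse the ordering: baseline adjustment was ahead in every calculation with a true effect.

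Fourth, a log-scale model may seem the natural remedy for a frequency. It is not dependable. Both arms are referred to detoxification and rehabilitation (section 3.3), so zeros at 6 months are plausible, and the simulations show log(1+count) losing power when they are common. This objection stands in full.

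**Conclusion.** The point holds in conditional form. The outcome is defined in two ways, its scale is not stated, and no analysis is assigned to it. If the one named continuous test is applied to the change, the result is valid but less precise than a baseline-adjusted comparison. The sample penalty is 1.11 to 1.67 times for rho 0.8 to 0.2 (normal theory, equal SDs); the power loss is about 7 to 42 points under the assumed skewed counts with 52 v 28. These sizes rest on assumed correlation, distribution, effect and retention, and they ignore session-group correlation.

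A reader might infer that the plan commits to a t-test on the raw difference of a skewed count and so forfeits much of its power. The documents do not support that: the test is inferred, the skew and the count scale are not stated, and at high correlation the loss can be small. Nor is there evidence of bias or of excess false positives. This is one secondary outcome in a 100-person feasibility trial with no stated power target, so the main conclusions are little affected.

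**What to change.** - **Sections 2.1, 2.3 and 8:** use one definition, last-30-day injection frequency at 6 months, and state the item's scale (injections, days or categories). Say what role the 1-month value has, if any.
- **Section 8.1:** name the analysis for this outcome: regression of the 6-month value on arm and baseline value, with small-sample-corrected robust errors and the session-group correlation already promised. Report the adjusted mean difference with a 95% interval.
- **Raw change:** keep it as a descriptive summary. Regressing the change on arm and baseline gives the same arm coefficient, so nothing is lost by the redefinition.
- **Sensitivity analysis:** a ratio-scale count model may be added, with attention to its type I error at this sample size. Do not make log(1+count) the main model.

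The cost is wording only. Drug use is already collected at baseline and 6 months, and the effect stays on the scale of a mean difference. If the item proves to be yes/no, state that instead and compare 6-month proportions.
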